3.3 Sample Size Considerations

While there is no statistical rationale for the sample size, it has been selected based on prior experience with generation 2.0 ASOs (Tabrizi et. al, 2019) given by IT bolus injection to ensure that the safety, tolerability, PKs, and exploratory pharmacodynamics will be adequately assessed while minimizing unnecessary patient exposure.

3.4 Statistical Methods

3.4.1 Patient Population Analyzed

The following analysis populations are defined for this study:

- ITT Population: All patients who are randomized and receive at least 1 dose of Study Drug (ISIS 814907 or placebo).
- Safety Population: All patients who are randomized and receive at least 1 dose of Study Drug (ISIS 814907 or placebo).
- PK Population: All patients who are randomized, receive at least 1 dose of ISIS 814907 and have sufficient sampling (at least one evaluable post-baseline PK sample) to permit PK evaluation.

The ITT population will be used for all demographic, baseline characteristics, PD and exploratory analyses. The safety population will be used for all safety analyses. PK population will be used for PK analyses.

A Per Protocol population may be considered for select analyses if necessary.

As previously indicated, the population will be used in conjunction with the analysis periods and analysis groups to uniquely indicate the subjects and data contributing to the analyses. For example, an analysis of the safety population in the Active Treatment Period for late start subjects will include data from the LTE period for subjects who were randomized and received at least one dose of study drug.

3.4.2 Handling of Missing Data

Unless otherwise specified, missing values will not be imputed.

3.4.3 Planned Interim Analysis

3.4.3.1 End of MAD, Part 1

An interim analysis of the MAD Period to investigate safety, PK, PD and exploratory endpoints will be conducted at the end of MAD, Part 1 when the last patient completes the last visit, and the results will be summarized by treatment group. Unblinded data will be evaluated at this analysis. All patients/all data through the end of MAD, Part 1 will be used for the analysis with the exception of CSF biomarkers data (through Day 1 pre-dose in LTE, Part 2). The individuals involved in the unblinded interim analysis will be identified and documented at the time of unblinded interim analysis according to Ionis standard operation procedure (SOP). The investigators, patients and study center personnel, including the site pharmacist, will be blinded to treatment assignment from the MAD for the duration of the study (i.e., until the end of LTE).

The MAD Period will be analyzed during this IA. The analysis of the LTE, MAD+LTE, and Active Treatment Periods will be performed following the final study lock after completion of the LTE period.

3.4.3.2 Safety monitoring review

A formal safety monitoring group (FSMG) will be assembled to review unblinded safety, tolerability, PK, and target engagement/PD (as needed) data collected during this study. The FSMG group is comprised of at least three medical doctors, all experienced in the conduct of clinical studies in patients with neurodegenerative diseases and otherwise independent from the conduct of the study. Unblinded statisticians or designees who will not be involved in the study conduct will generate and distribute the data to the FSMG prior to each meeting. Based on its ongoing assessment of the study data, the FSMG will provide recommendations to the Sponsor for modifying, stopping or continuing the study as planned. Details on the assessments, frequency of review, meeting schedules and controlled access to unblinded data will be outlined in the FSMG charter.

3.4.4 Demographic and Baseline Characteristics

Demographic and Baseline characteristics will be summarized using descriptive statistics by analysis group based on the ITT population for the MAD, LTE and Active Treatment Periods separately.

Demographics include age, gender, ethnicity, race, education level in ISCED, weight, height, BMI. Height was measured at MAD Screening only, at other visits other than Screening, BMI (kg/m²) could be computed using the formula:

BMI = (weight in kilograms) / [height in cm / 100]².

Baseline characteristics include individual patient CSF volume (spinal CSF volume, cranial CSF volume, and total CSF volume) and brain volumes (whole brain, ventricular, left and right hippocampal volumes), ARWMC total score; C-SSRS suicidal ideation score and clinical assessment scales (RBANS, MMSE, FAQ, NPI-Q, MHIS, CDR global and memory score, CDR Sum of Boxes, GDS-SF); CSF AD biomarkers (total tau, phospho-tau, A-beta42), CSF NfL & total NfH; prior and concomitant anti-dementia medication (cholinesterase inhibitors and memantine), estrogen replacement therapy, low dose antipsychotic medication, aspirin, fish-oil; and genetic profile (APOE, CD33, BCHE, H1 MAPT haplotype).

3.4.5 Disposition of Subjects

Patient enrollment and disposition for the MAD and LTE Periods will be summarized for each treatment group, and for all patients. By-subject disposition listings for all randomized subjects and for screen failures will also be provided for the MAD and MAD+LTE Periods.

- The summaries for the MAD Period will include: the total number of screened patients, the number of patients screen failures, the number and percentage of randomized patients, the number and percentage of patients in each analysis population the number and percentage of patients who completed the study treatment, the number and percentage of patients who terminated treatment and reason, the number and percentage of patients who completed post-treatment follow-up, and the number and percentage of patients who terminated post-treatment follow-up and reason.
- The summaries for the LTE Period will include: the number of patients that transitioned into the LTE (i.e., total number, and breakdown of number of patients by MAD dose cohort), the number of patients that did not transition into the LTE and reason, the number of patients who were registration screen failures and reason for Cohorts A and B, the number and percentage of patients in each analysis population, the number and percentage of patients completed the study treatment, the number and percentage of patients who terminated treatment and reason, the number and percentage of patients completed post-treatment follow-up, and the number and percentage of patients terminated post-treatment follow-up and reason.

Study terminations and LTE registration screen failures that are due to COVID-19 related impact will be included in the above-mentioned summary tables and subject listings.

3.4.6 Protocol Deviations

Protocol deviations will be classified to major or minor based on the study protocol deviation process plan. Protocol deviations will be provided in the data listings. Additional table may be provided to summarize the protocol deviations related to COVID-19.

A listing of all patients affected by the COVID-19 related study disruption by subject number identifier and by investigational site, and a description of how the individual's participation was altered will be provided.

Listing of medical history will be provided.

Subject listings will be performed for the MAD and MAD+LTE Periods.

3.5 Safety Analyses

The safety analyses for the MAD Period, the LTE Period, and the Active Treatment Period will be conducted on the Safety Population.

3.5.1 Exposure

Treatment duration, total amount of study drug (MAD: ISIS 814907 or placebo; LTE and Active Treatment periods: ISIS 814907) received (mg), and number of doses administered will be summarized by analysis group for the MAD, LTE, and Active Treatment Periods.

The treatment duration (days) for each subject is defined as:

- MAD Period, LTE Period separately: last dose date within the Period first dose date within the Period + 1
- Active Treatment Period, early starters: [(last dose date in MAD first dose date in MAD + 1) + (last dose date in LTE first dose date in LTE + 1)]. For subjects not enrolled in LTE then it is the same as the MAD Period exposure
- Active Treatment Period, late starters: (last dose date in LTE first dose date in LTE + 1).

3.5.2 Time on Study Analysis

The time on study analysis described below will be included in the final analysis only.

Time on study (years) will be summarized by analysis group for the MAD, LTE, MAD+LTE and Active Treatment Periods using descriptive statistics. Total time on study (patient-years) in each analysis group will be included in the summaries.

Additionally for the MAD+LTE Period, time from last dose date in MAD to first dose date in LTE (years), and time from last study visit date in MAD to first dose in LTE (days and years, separately) will be summarized by analysis group using descriptive statistics.

Time on study (days) for each subject is defined as:

- MAD Period, LTE Period separately: last study visit date within the Period first dose date within the Period + 1
- Active Treatment Period, early starters: (last study visit date in MAD first dose date in MAD + 1) + (last study visit date in LTE first dose date in LTE + 1). For subjects not enrolled in LTE then it is the same as the MAD Period time on study.
- Active Treatment Period, late starters: last study visit date in LTE first dose date in LTE + 1.
- MAD+LTE Period: (last study visit date in MAD first dose date in MAD + 1) + (last study visit date in LTE first dose date in LTE + 1). For subjects not enrolled in LTE then it is the same as the MAD Period time on study.

Time on study (years) for each subject is calculated as the time on study (days) divided by 365.25. Total time on study (patient-years) is calculated as the sum of time on study (years) across subjects within the analysis group and period.

For the MAD+LTE Period: Time from last dose date in MAD to first dose date in LTE (years) is defined as: (first dose date in LTE – last dose date in MAD + 1)/365.25. Time from last study visit date in MAD to first dose in LTE (days) is defined as: first dose in LTE – last study visit

date in MAD + 1; Time from last study visit date in MAD to first dose in LTE (years) is: (first dose in LTE – last study visit date in MAD + 1)/365.25.

3.5.3 Adverse Events

3.5.3.1 MAD Period and LTE Period

The incidence (proportion) of treatment-emergent adverse events (TEAEs) will be summarized for the MAD and LTE Periods separately, and incidence (rates) of TEAEs will be summarized for the Active Treatment period where indicated by *. The Medical Dictionary for Regulatory Activities (MedDRA) version 20.0 will be used. Summaries will be presented by preferred term (PT) and system organ class (SOC), unless otherwise indicated, for:

- Any TEAE* (summarized by PT only and by both SOC and PT)
- TEAEs potentially related to Study Drug. Related is defined as "Related", "Possible", or missing relationship to study drug, as determined by the investigator
- TEAEs potentially related to Lumbar Puncture (LP) procedure. Related is defined as "Related", "Possible", or missing relationship to LP procedure
- Any TEAE by severity*. At each level of subject summarization, a subject is classified according to the highest severity if the subject reported one or more events. TEAEs with missing severity will be categorized as "Missing" for this summary
- TEAEs potentially related to Study Drug by severity
- TEAEs potentially related to LP procedure by severity
- Serious TEAEs* (by PT only and by both SOC and PT)
- Serious TEAEs potentially related to Study Drug*
- Serious TEAEs potentially related to LP procedure*
- TEAEs leading to permanent study drug discontinuation* (by PT only and by both SOC and PT)

The number and proportion of LPs leading to TEAEs will be summarized for the MAD and LTE Periods separately. The severity of AEs and SAEs will be graded based on criteria from the Common Terminology Criteria for Adverse Events (CTCAE) Version 4.03, June 2010. SAEs and non-serious AEs that lead to permanent study drug discontinuation will be listed separately. Non-treatment emergent adverse event will be flagged in the data listing.

An adverse event will be regarded as treatment emergent if it is present prior to receiving the first dose of study drug (MAD: ISIS 814907 or placebo; LTE and Active Treatment Periods: ISIS 814907) and subsequently worsened, or is not present prior to receiving the first dose of

study drug (MAD: ISIS 814907 or placebo; LTE and Active Treatment Periods: ISIS 814907) but subsequently appeared.

If there is no "Formlink" link, and the AE (start date/time) occurs after the subject's first dosing date/time, then the AE is treatment-emergent. Otherwise, if the AE (start date/time) occurs prior to the subject's first dosing date/time, then the AE is not treatment-emergent.

If there is a "Formlink" link between two AE records, then we compare them pairwise, and consider two cases, where we compare the AE severity (mild/moderate/severe) between the two records in the pair. We chronologically order the 2 records (by AE start date) and refer to the "first" and "second" AEs.

Case 1: The first AE record in the pair occurs before first dosing, and the second AE record occurs after first dosing.

If the AE severity or seriousness of the second record is worse than that of the first record, then only the second AE is deemed as TEAE. Otherwise, neither record is considered as TEAE.

Case 2: Both AE records in the pair occur after first dosing.

The worst AE will be deemed as a TEAE.

All TEAEs identified based on the rules above will be summarized in the event number analysis.

The most conservative approach will be used to determine if the event occurs after the treatment. For example, if the onset date or resolution date of an AE is prior to the first study treatment date, it will be considered to have occurred prior to the study period. If the onset or resolution date of an AE is a partial date with only month or year available or completely missing, then the event is assumed to be within the study period unless the year is prior to the year of the first study treatment date, or if in the same year, the month is prior to the month of the first study treatment date.

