9.4.3.5 Outcome of the Adverse Event

If the event is a non-serious AE, then the event's outcome is characterized by 1 of the following:

- AE Persists: Patient terminates from the trial and the AE continues
- **Recovered:** Patient recovered completely from the AE
- **Became Serious:** The event became serious (the date that the event became serious should be recorded as the Resolution Date of that AE and the Onset Date of the corresponding SAE)
- Change in Severity (if applicable): AE severity changed

If the event is an SAE, then the event's outcome is characterized by 1 of the following:

- Ongoing: SAE continuing
- **Persists (as non-serious AE):** Patient has not fully recovered but the event no longer meets serious criteria and should be captured as an AE on the non-serious AE eCRF (the SAE resolution date should be entered as the date of onset of that AE)
- **Recovered:** Patient recovered completely from the SAE (the date of recovery should be entered as the SAE resolution date)
- Fatal: Patient died (the date of death should be entered as the SAE resolution date)

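### The linked-record rule for treatment-emergent AEs can leave an SAE out of the serious TEAE tables, or a higher grade out of the severity table, and in chains can flag an event that never exceeded its pre-dose severity

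*Combined protocol and SAP*

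**What the plan says.** SAP 3.5.3.1 gives a general definition and then an operational rule.

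- **Definition.** An AE is treatment-emergent if it first appears after the first dose, or if it "is present prior to receiving the first dose of study drug" and later gets worse.
- **Linked records.** Where the data carry a Formlink "link between two AE records, then we compare them pairwise". The lead-in to both cases names one criterion: "where we compare the AE severity (mild/moderate/severe) between the two records in the pair".
- **Case 1** (first record before first dose, second after). The test is "If the AE severity or seriousness of the second record is worse than that of the first record". If it is met, only the second record is a TEAE; otherwise neither is.
- **Case 2** (both records after first dose). The whole rule is "The worst AE will be deemed as a TEAE".
- **Counting.** "All TEAEs identified based on the rules above will be summarized in the event number analysis".

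Protocol 9.4.3.5 explains why linked records exist. When a non-serious AE becomes serious, "the date that the event became serious should be recorded as the Resolution Date of that AE", and the same date starts a corresponding SAE record. An SAE that stops being serious but persists is likewise closed and continued as a non-serious AE. A change in severity is also an outcome category.

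**The concern.** Case 2 names one record of the pair as the TEAE. The SAP's rule for unlinked records does not apply to the other record, so nothing in the text makes that one a TEAE. Which record survives depends on *worst*, which Case 2 does not define. The only criterion stated for it is the lead-in's severity comparison. Seriousness is named in Case 1 and not in Case 2, and there is no tie rule.

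Safety is the primary objective, and the TEAE flag feeds several outputs: the serious TEAE tables, the serious TEAE tables by relationship to drug and to lumbar puncture, the by-severity tables, and the Active Treatment Period incidence rates in SAP 3.5.3.2. Two competent programmers could derive different serious TEAE tables from this text.

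Separately, the rule handles two records at a time. The protocol's record handling can produce longer sequences, such as AE to SAE and back to AE, and the SAP does not say how these are judged against the pre-dose state.

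**Working it through.** The documents give no figure to reproduce. The check runs the written rule through every severity combination, with mild = 1, moderate = 2 and severe = 3. The counts are logical combinations, not expected frequencies.

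**1. Case 2 pairs: non-serious record, then SAE record, both post-dose.** There are 3 × 3 = 9 severity combinations.

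| SAE record compared with first record | Combinations | If severity decides | If seriousness decides |
|---|---|---|---|
| More severe | 3 | SAE flagged | SAE flagged |
| Same severity | 3 | Tie, no rule | SAE flagged |
| Less severe | 3 | Non-serious record flagged, SAE not | SAE flagged, higher grade not |

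On severity alone, 3 + 3 = 6 of 9 do not securely reach the serious TEAE tables. If seriousness counts, as in Case 1, the figure is 0 of 9, but in the bottom row the higher grade is lost from the by-severity table. A severe non-serious AE followed by a moderate SAE therefore loses something whichever way *worst* is read, because only one record is kept.

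**2. Three-record chains: one pre-dose, two post-dose, all non-serious.** There are 3³ = 27 sequences. Those never worse than pre-dose number 1 + 4 + 9 = 14 (pre-dose mild, moderate, severe). Case 2 applied to the two post-dose records gives a definite TEAE in 8 and a tie in 6. Five of the 14 change severity at each step:

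| Pre, post, post | Case 1 on records 1 and 2 | Case 2 on records 2 and 3 | Flagged record against pre-dose |
|---|---|---|---|
| Moderate, mild, moderate | Neither | Record 3 | Equal |
| Severe, mild, moderate | Neither | Record 3 | Lower |
| Severe, mild, severe | Neither | Record 3 | Equal |
| Severe, moderate, mild | Neither | Record 2 | Lower |
| Severe, moderate, severe | Neither | Record 3 | Equal |

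All five are flagged. Comparing every pair does not help: set against the pre-dose record, Case 1 says the flagged record is not a TEAE while Case 2 says it is, and no precedence is stated. In the fourth row the two cases disagree about record 2 even when only successive records are compared.

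**3. Scale of one misclassification.** Cohorts of 8, 8, 12 and 16 at 3:1 give planned active MAD groups of 6, 6, 9 and 12. If the patient has no other qualifying event in that table row, one patient moves the incidence by 1/6 = 16.7, 1/6 = 16.7, 1/9 = 11.1 or 1/12 = 8.3 percentage points. The same holds for any single misclassified patient, so this says nothing about how often the error occurs.

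**The case against.** **The text may intend seriousness to count in Case 2.** The severity lead-in also introduces Case 1, where seriousness plainly counts, so it need not be exclusive. This stands: *worst* is undefined, and a reader who infers that the SAP selects by severity alone goes further than the text. But the charitable reading moves the loss to the severity table and does nothing for chains.

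**Chains rest on inference.** A reader might conclude that only neighbouring records are compared, or that every severity change opens a new record. The SAP says pairwise, not neighbouring, and protocol 9.4.3.5 lists a severity change as an outcome without saying that a new record opens. The five chains assume that it does. The protocol does expressly open new records when an AE becomes serious and when an SAE persists as non-serious, so sequences of three are foreseeable.

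**The definition is not flatly contradicted.** It requires worsening but does not fix the reference point, and a move from mild to moderate after dosing is literally a worsening. Such flags also over-report rather than hide harm. *In tension with* is the accurate description. A simple pre-dose and post-dose pair is handled properly by Case 1.

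**SAEs are reported elsewhere.** SAP 3.5.3.1 lists SAEs separately, protocol 10.6.2 calls for narratives of serious AEs, and the protocol synopsis sends all SAEs to the Formal Safety Monitoring Group. This stands and limits the consequence. In an untied pair the patient also stays in the any-TEAE incidence, because one record is still flagged.

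**Conclusion.** The rule should be changed. Keeping one record of a post-dose pair can leave an SAE out of the serious TEAE tables and rates, or leave a higher grade out of the by-severity table. Applying a two-record rule to longer chains can flag an event that was never worse than before dosing.

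A reader might infer that SAEs disappear from the trial's reporting, or that fluctuating pre-existing events are routinely counted as new. The documents support neither. The effect is confined to tables and rates, and the second error needs at least three linked records. Frequency cannot be estimated from the documents.

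The conclusion assumes that the record not named in Case 2 is left unflagged, as the counting sentence implies. The 6-of-9 figure also assumes that severity alone decides Case 2, and the chain result assumes that successive severity changes are held as linked records.

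**What to change.** In SAP 3.5.3.1, replace the two cases with a rule for the event as a whole:

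- Treat each set of linked records as one event.
- Call it treatment-emergent if there is no pre-dose record, if any post-dose record is more severe than the worst pre-dose record, or if any post-dose record is serious when no pre-dose record was.
- Count it once. Carry into the tables the highest post-dose severity, and *serious* if any post-dose record is serious, unless the event was already serious and at least as severe before dosing.

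Under this rule all 9 non-serious-to-serious combinations keep both the SAE and the highest grade, and none of the 14 never-worse chains is flagged.

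Two simpler repairs do not work. Ranking by seriousness first and still keeping one record drops the severe grade when a severe non-serious AE is followed by a moderate SAE. Comparing with the last pre-dose record, rather than the worst, flags an event that was severe and then mild before dosing and moderate after it.

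The cost is a few lines of SAP text and a change to the TEAE derivation. No new data are needed.
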